We cannot accurately estimate the risk of bladder or rectal injury as detailed analysis of the currently reported patient experience has not been reported. We have visited both the group in Lisbon, who have now treated over 250 patients and the Brazilian group has treated over 70 patients. There have been no serious rectal injuries reported. There has been one injury in the Lisbon group to the bladder that resulted in the need for bladder resection.

Therefore, the current experience would suggest that the risk of complication is low, with the risk of a serious complication is extremely low (less than 1% chance) but that is based on clinical experience and not careful assessment of the rectum and bladder. This is the main focus of our study

Based on the reported data to date and known potential complications of angiographic procedures, the following are potential risks of the procedure:

Related to the embolization of the prostate: Minor or self-limited complications: burning in the urethra, urinary

infection, hematuria, hematospermia, hemorrhage, vasospasm, rectorrhagia, pain in the pelvis, or allergic reaction to embolic material.

More serious complications related to embolization of the prostate: bladder or bladder neck necrosis, possibly requiring surgical resection. Bladder ischemia causing severe pain, but resolving without complication. Other than the one case of surgical resection of the bladder in Lisbon, all reported complications have resolved with minimal or no therapy.

Complications related to angiography: arterial injury, which in rare instances (<1%) can lead to need for surgical repair of the artery, arterial injury in the pelvis, puncture site hematoma and allergic reaction to the contrast media.

Radiation injury to the skin of the buttocks- this complication is not yet reported but is possible with prolonged procedures.

Risk Minimization

As noted above, great care will be taken with the use of X-ray exposure to minimize dose. Similarly, each patient will be evaluated pre-procedure for sedation risk according to the standard of care and will be followed by both the interventional radiology and urology staff physicians.

Each significant injury to a patient's bladder or rectum will be reported immediately to the IRB staff. Those with lesser injuries will be recorded and followed to resolution. All minor and major complications will be summarized after each set of 10 patients and reported to the IRB. We currently plan to stop the study for re-evaluation of its overall safety if more than 20% of patients assessed after the first 10 patients (and each subsequent group of 10 patients) suffers either a bladder or rectal injury requiring surgical intervention.

We do not believe a data safety and monitoring committee is needed as our urology co-investigators will serve the role of safety monitors. They have a strong incentive to identify injuries, as they do not perform this procedure and it has the potential to compete with traditional therapies. While our urology colleagues are interested in providing alternatives to TURP for their patients, they have no interest in a therapy that is not safe.

7. Does a Data Safety and Monitoring Board exist?

Yes No

[A Data Safety and Monitoring Board, an independent group of experts, will review the data from this research throughout the study. Patients will be told about new information from this or other studies that may affect their health, welfare, or willingness to stay in this study.]

8. Does this study include a Placebo?

Yes No

9. Website Summary: If this is an open clinical trial, recruitment material for clinical trials and information for sponsors about the type of research we do will be posted on the Clinical Trials website. Please create a brief summary, in Layman Terms (8th grade language) of 200 words or less for this protocol outlining the salient features that may be useful to public and health care professionals.

<http://clinicaltrials.georgetown.edu/index.html>

The Departments of Radiology and Urology at Georgetown University Hospital are collaborating on a research study to determine the safety and effectiveness of prostate embolization, a new treatment for men who have enlarged prostate glands and urinary obstruction. Men with urinary obstruction usually have frequent urge to urinate, a weak urine stream, difficulty starting to urinate and may need to urinate numerous times each night.

Prostate enlargement (medically known as benign prostatic hyperplasia) is due to overgrowth of the prostate gland tissue and is very common in older men. This is not related to prostate cancer, although all patients treated in this study and for prostate enlargement in general are screened to be sure there is no evidence of prostate cancer.

The new treatment, prostate artery embolization, is a minimally-invasive procedure done while a patient is sedated. After local anesthesia, the artery at the top of the leg is entered with a catheter (a thin long tube), which is then advanced into the arteries feeding the prostate gland. Small beads are injected into the arteries to block the blood supply to the prostate tissue, causing that tissue to shrivel and shrink. The procedure takes from 2 to 3 hours and will require only an overnight observation stay in the hospital. The patient can return to normal activities within a day or two of treatment.

There are no studies on prostate artery embolization that have been completed in the United States. The studies that have been completed in other countries to date suggest that this is effective in most men in causing the urinary symptoms to significantly improve or disappear. The data so far also suggests that this is safe, with few complications.

This study will focus first on the safety of the procedure to be sure there are no injuries to other pelvic structures, such as the bladder or rectum, which are very near the prostate. The current experience in other countries suggests that these types of injuries are very rare, but we plan on a detailed analysis to accurately assess the risk. The study will also measure the severity of symptoms before and after the procedure and to evaluate whether the prostate shrinks and the extent of scarring of the prostate tissue.

With any treatment, the long-term outcome is also a key question. There are no long-term studies of this procedure yet completed. We hope to follow patients treated for up to 5 years after treatment by questionnaire to determine if once gone, the symptoms ever return.

10. Data Safety and Monitoring Plan

10.1 Assignment of Risk Levels – Please select the risk level for your study and check the boxes that apply.

10.1.A Research involving minimal risk only if one of the following applies:

	Anthropomorphic evaluations		DEXA scans
	Electrocardiograms (EKGs)		Exercise testing
	Intravenous glucose tolerance tests		Intravenous catheter insertion
	Magnetic resonance imaging (MRI) scans		Observational studies
	Oral glucose tolerance tests		Pathology slide review
	Special/prescribed diets		Venipuncture
	Other non-therapeutic tests or studies. Please list:		

Note: In the assignment of risk levels, a research survey may be considered more than minimal risk to subjects if dealing with very sensitive information.

10.2 Plans for Reporting of Adverse Events Including Subject’s Death.

Adverse events from this protocol will need to be reported to the IRB, GCRC RSA (if the study is being conducted on the GCRC), and GCRC Nurse Manager (if the study is being conducted on the GCRC). In the section below, please list other individuals and/or entities to whom adverse events will be reported.

Individual/Entity	
	Investigator
	National Institutes of Health and/or
	Food and Drug Administration (FDA)
	Other agency or sponsor
	Please specify:

10.2.1 Who is the individual/entity primarily responsible for AE and to whom they are primarily reported.

Name	Position
[name]	Principal Investigator

Plans for Monitoring the Progress of Trials and the Safety of Participants

10.2.1 Safety tests. In the section below, please indicate the summary of safety tests, particularly those that screen out ineligible research subjects and those that monitor for toxicity and other adverse outcomes.

Clinical evaluation will be used before to exclude those that have renal insufficiency, iliac artery occlusion, and prostate cancer.
 
Office anoscopy and cystoscopy will be completed before the procedure and at regular intervals after to evaluate the bladder and rectal mucosa. This is the most sensitive test to detect ischemic injury.

All X-ray parameters will be recorded to estimate patient exposure. At the 1 week and 3 month office visits, each will have the skin of the buttock assessed, as this is the most likely site for an radiation injury and it should be manifest between 1 week and 3 months after exposure.

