This is a Phase I-II study with the primary goal of determining the safety of prostatic artery embolization (PAE) for benign prostatic hyperplasia. Our primary outcome is the frequency of adverse events, particularly bladder and rectal complications, which may occur as a result of this procedure. Secondly, the study will allow us to begin to determine its effectiveness in diminishing obstructive symptoms associated with BPH.

Duration of investigation

The investigation will enroll 30 patients, with a target enrollment period of less than 12 months. Each patient will be consented for follow-up up to 5 years, but each patient will reach the first important safety endpoint 1 week after treatment and the first clinical efficacy assessment 3 months after treatment.

Written Protocol*Objectives*

To determine the safety and effectiveness of prostate artery embolization for the treatment of BPH.

Description of study type

This is a prospective observational non-comparative study of an initial cohort of 30 patients.

Study Population

The patients will be recruited from the urology practice at Georgetown University and from other urologists in the area and by patient self-referral. The study will be registered at clinicaltrials.gov and also will be announced on a study website, the content of which will be approved by the IRB at Georgetown University Medical Center

and both of these sites may lead patients to self-refer for participation.

Patient Inclusion Criteria

1. Men presenting with benign prostatic hyperplasia with symptoms for at least 6 months that are refractory to medical management or in whom medications are contraindicated, not tolerated or refused. Additional criteria include:
 - a. Moderate to severe obstructive urinary tract symptoms as defined as an International Prostate Symptom Score (IPSS) score of 12 or greater.
 - b. Peak urinary flow (QMax) of less than 12 mL/s or acute urinary retention.
 - c. Prostate volume of greater than 50 cc and less than 100 cc.
 - d. Minimum age of 50 years, maximum age of 90 years

Exclusion Criteria

1. Presence of prostate cancer based on digital rectal exam (DRE), biopsy, Transrectal Ultrasound (TRUS), PSA > 10 ng/mL.
2. Renal insufficiency (serum creatinine of greater than 1.8 mg/dL)
3. Prior prostate surgery or intervention, including trans-urethral resection of the prostate, balloon dilation, stent implantation, laser prostatectomy, or hyperthermia

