- a. IPSS will be administered
- b. Urine analysis, culture, sensitivity (if indicated)
- c. Blood chemistry (including blood count, BUN, serum creatinine)
- d. A baseline serum prostate specific antigen (PSA).
- e. A focused urologic physical examination, including a rectal exam and trans-rectal ultrasound to detect prostate volume.
- f. The patient will complete uroflowmetry, including voided volume (>125cc), total time of voiding, peak urine flow rate, average urine flow rate, and post-void residual volume.

If either physical examination or PSA suggests possible prostate cancer, trans-rectal prostate biopsy will be performed. If prostate cancer is detected, the patient will be excluded.

Provided participants are not excluded based on the above evaluation, at a separate visit, each will have:

- a. Anoscopy and cystoscopy in the urology clinic to ensure that these are normal, without mucosal abnormality.
- b. A baseline contrast-enhanced MRI of the prostate will be completed.
- c. The patient will also complete a 5 question sexual function questionnaire, the International Index of Erectile Function (IIEF). This questionnaire and the IPSS are described in detail in a later section.
- d. Each patient will have a consultation visit with one of the interventional radiologist co-investigators. The patient will have a focused physical examination, including vascular exam, and will have the procedure explained in detail. The procedure will be scheduled at that time.

Procedure

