IPSS and IIEF Questionnaires Medical History Physical Exam CBC, Blood Chemistry, PSA UA, Urine C&S (if indicated) Urologic exam Urine Flowmetry Cystoscopy Anoscopy MRI (if not able, TRUS)	2 hour procedure Sedation Bladder catheter (removed prior to discharge) Overnight stay Symptom assessment Adverse Event Assessment	IPSS Questionnaire Symptom Questionnaire Urologic Exam CBC, Blood Chemistry, PSA UA, Urine C&S Cystoscopy Anoscopy* Urine Flowmetry Adverse Event Assessment	IPSS and IIEF Questionnaires Urologic Exam CBC, Blood Chemistry, PSA UA, Urine C&S Urine Flowmetry Cystoscopy MRI (if not able, TRUS) Adverse Event Assessment	IPSS and IIEF Questionnaires Urologic Exam CBC, Blood Chemistry, PSA UA, Urine C&S Urine Flowmetry Cystoscopy MRI (if not able, TRUS) Adverse Event Assessment	IPSS and IIEF Questionnaires Urologic Exam CBC, Blood Chemistry, PSA (PSA only after 12 months) UA, Urine C&S Urine Flowmetry Cystoscopy (12 month only) MRI (if not able, TRUS) Adverse Event Assessment

*repeat anoscopy at subsequent visits until resolves or stable for two consecutive examinations.

Outcome Assessment Measures

Laboratory Assessment

The safety of the therapy will be monitored in part using laboratory analyses, including CBC, serum chemistry, urinalysis, urine culture and PSA. Of these, the urine testing is directed at assessing bladder function, while PSA trending will be an important outcome measure of prostate status.

Urine Flowmetry

Several tools have been developed to evaluate severity of LUTS and to track disease progression and response to therapy. Urine flowmetry, which includes voided volume (>125cc), total time of voiding, peak urine flow rate (Q_{max}), average urine flow rate, and post void urinary volume, provides an objective measure of urinary function and will be measured in this study [29].

Symptom and quality of life assessment

While urinary symptoms are increased in larger prostates, prostate size does not always predict severity of symptoms. Many patients with enlarged prostates do not have symptoms and therefore no therapy other than

watchful waiting is indicated.

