Trans rectal ultrasound is the current standard imaging for the clinical assessment of the prostate gland [29]. Having said that, MRI can provide a more comprehensive assessment of the prostate size and tissue viability. Contrast-enhanced MRI provides a perfusion “map” of the prostate and allows the determination of the extent of infarction (or non-perfusion) of the prostate. The preliminary work in both Lisbon and Sao Paulo suggests that the greater the degree of de-vascularization of the prostate, the greater the volume reduction. This is likely to correlate with symptom improvement, although this requires confirmation. We believe that this study will provide preliminary data that can be used to help design studies to test that hypothesis.

Adverse Events

Each adverse event will be recorded as they occur. Each will be categorized as to type and severity using the Society of Interventional Radiology (SIR) definitions of adverse events based on outcome. That classification is as follows:

Type	Class	Definition
Minor	A	No therapy, no consequence
	B	Nominal therapy, no consequence; includes overnight admission for observation only.
Major	C	Require therapy, minor hospitalization (<48 hours).
	D	Require major therapy, unplanned increase in level of care, prolonged hospitalization (>48 hours).
	E	Permanent adverse sequelae.
	F	Death.

Analysis

The primary outcome is the absence of complications to the bladder, rectum or other pelvic structures detected in the first week after therapy. Each patient will be judged free of these adverse events or not. For those with an adverse event, the complication will be scored using the SIR definitions. Descriptive statistics will be used to summarize these events, along with patient demographics and initial clinical status.

Appropriate parametric and non-parametric tests will be used to assess change in laboratory measures, urine flowmetry parameters, and scores from the IPSS and IIEF. Changes in prostate volumes and the estimated volume of devascularized tissue will be calculated for each patient and outcomes from the different embolics will be compared. Appropriate paired parametric and non-parametric tests will be used to determine statistical significance. A p value of 0.05 will be considered statistically significant.

Statistical Considerations (justification for sample size or “n”, power or degree of change):

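### The single IPSS and Qmax that qualify a man are also his only pre-treatment values, so in this uncontrolled study regression to the mean biases the change in both toward benefit

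*Combined protocol and SAP*

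**What the plan says.** Patient Inclusion Criteria 1a requires an "International Prostate Symptom Score (IPSS) score of 12 or greater". Criterion 1b requires "Peak urinary flow (QMax) of less than 12 mL/s or acute urinary retention". Both cut-offs are one-sided, but 1b has a second route that does not depend on flow.

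Under Pre-procedure Patient Evaluation, the first list (the urologist's evaluation) contains "IPSS will be administered" and one uroflowmetry. Men can still be excluded at that stage. The section continues: "Provided participants are not excluded based on the above evaluation, at a separate visit, each will have" anoscopy and cystoscopy, a contrast MRI, the IIEF and a consultation. That second list has no IPSS and no flow.

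Table 2 has one pre-treatment column, with one IPSS and one flowmetry. The study is described as non-comparative, with 30 patients. Improvement in IPSS and in Qmax are secondary objectives. The Analysis section assesses change with parametric and non-parametric tests, paired where significance is judged, and adds: "A p value of 0.05 will be considered statistically significant". The text available for review mentions no run-in, repeat baseline or adjustment for selection.

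**The concern.** A man whose IPSS happens to be high on the day, or whose flow happens to be low, is more likely to qualify. On remeasurement, the chance part of that reading is on average no longer there. If change is counted from the qualifying reading, the group appears to improve even when nothing has happened. A concurrent control arm would show the same drift and cancel it, but this study has none.

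The effectiveness evidence here is before-and-after change judged at p = 0.05. A small bias matters to such a test when it is not small beside the standard error of the mean change. For Qmax the documents cite no expected mean change to set the bias against.

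**Working it through.** **Is the qualifying value the baseline?** The documents do not attach the word baseline to these two measurements. This is therefore an inference from the schedule, but a firm one: the first evaluation has one IPSS and one flow, the second visit has neither, and Table 2 has a single pre-treatment column.

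**Stated figure to reproduce.** None. The Statistical Considerations section gives no power, effect size, SD or reliability.

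**Inputs from the documents.** IPSS cut-off 12, Qmax cut-off 12 mL/s, n = 30, significance level 0.05 (taken as two-sided, since this is not stated).

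**Assumed inputs**
- IPSS before selection: mean 16 to 22, SD 6 to 7, reliability 0.7 to 0.9.
- Qmax before selection: mean 7 to 12 mL/s, SD 3.5 to 4.5, reliability 0.6 to 0.8.
- Normal true scores and independent errors at each occasion, with every man selected on the measure concerned.

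**Formula.** With z = (cut-off − mean)/SD, the expected spurious improvement is

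(1 − reliability) × SD × φ(z)/P,

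where P = 1 − Φ(z) for IPSS (selected above) and P = Φ(z) for Qmax (selected below).

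**Worked values**
- IPSS, mean 16, SD 7, reliability 0.7: z = −0.571; 0.3 × 7 × 0.3388/0.7161 = 0.99 points.
- IPSS, mean 22, SD 6, reliability 0.9: z = −1.667; 0.1 × 6 × 0.0995/0.9522 = 0.06 points.
- Qmax, mean 7, SD 4.5, reliability 0.6: z = 1.111; 0.4 × 4.5 × 0.2152/0.8667 = 0.45 mL/s.
- Qmax, mean 9, SD 4.5, reliability 0.6: z = 0.667; 0.4 × 4.5 × 0.3194/0.7475 = 0.77 mL/s.
- Qmax, mean 12, SD 4.5, reliability 0.6: z = 0; 0.4 × 4.5 × 0.3989/0.5 = 1.44 mL/s.

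**Rejection rates.** These come from simulated trials of 30 men with zero treatment effect and a two-sided paired t-test. The nominal rate is 5%.

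| Measure | Mean before selection | Spurious improvement | Test rejects |
|---|---|---|---|
| IPSS | 16 to 22 (whole range) | 0.1 to 1.0 points | 5 to 17% |
| IPSS | 20 to 22 | 0.1 to 0.5 points | 5 to 8% |
| Qmax | 7 | 0.1 to 0.5 mL/s | 6 to 10% |
| Qmax | 9 | 0.2 to 0.8 mL/s | 8 to 19% |
| Qmax | 12 (at the cut-off) | 0.6 to 1.4 mL/s | 28 to 53% |

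Where the rate is well above 5%, nearly all rejections are in the direction of benefit. The reason shows in one case: for Qmax with mean 12, SD 4 and reliability 0.6, the bias is 1.28 mL/s and the standard error of the mean change about 0.61. Their ratio, about 2.1, is close to the critical t value, so about half of such trials reject.

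**Yardstick for IPSS.** The background cites a mean fall of 6.5 points in an earlier uncontrolled series of 15 men. Even with a less favourable set (mean 12, SD 6, reliability 0.6), the bias is 0.4 × 6 × 0.798 = 1.91 points, or 1.91/6.5 = 29% of that fall.

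**Check of the remedy.** When an independent second pre-treatment value is the baseline, the mean spurious change is within about 0.02 of zero and rejection returns to about 5% in every scenario.

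**The case against.** The strongest case against is that the bias is probably small and that little depends on it.

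- **Men may sit well past the cut-offs.** In the background, an earlier series counted an IPSS below 20 and/or a Qmax above 7 mL/s as success, and a single reported case started at IPSS 24. The inclusion criteria also require at least six months of symptoms. This suggests the lower rows of bias, without proving them. It stands as a reason not to quote the upper bounds alone: 53% needs a pre-selection Qmax mean at the cut-off, so that half of the men evaluated would fail on flow, together with reliability of 0.6.
- **The retention route.** Men admitted through acute retention are not selected on Qmax, so the Qmax figures overstate the bias in proportion to their number. This stands.
- **Only secondary outcomes are touched.** This stands. The primary outcome is bladder, rectal and pelvic complications in the first week, and no sample size or stopping rule uses IPSS or Qmax.
- **A clean baseline would not make p < 0.05 evidence of a treatment effect.** Also true: placebo response and natural change would remain. But regression to the mean is the one component that the schedule can largely remove at little cost.

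A reader might infer that regression to the mean could account for an IPSS improvement of the size reported elsewhere, or that a significant Qmax result here is as likely false as not. The documents support neither. The first fails against the 6.5-point yardstick, and the second holds only in the most extreme scenario.

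**Conclusion.** The point holds in limited form. One-sided cut-offs applied to a single reading, reuse of that reading as baseline, paired tests and no comparator together bias the IPSS and Qmax changes toward benefit. The direction follows from the design, given any measurement noise.

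The size cannot be fixed from the documents. For IPSS it is at most about one point over the assumed range of means (16 to 22), and close to negligible if most men score around 20 or more. For Qmax it is modest if the mean is 7 to 9 mL/s and serious only if men cluster near 12.

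Two further unknowns remain. The share of men entering through retention is not given. Nor do the documents say whether the qualifying readings come before or after the drug-free periods in exclusion 8, which could shift the change either way.

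This is a worthwhile, inexpensive correction to secondary efficacy. It does not undermine the safety objective.

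**What to change.** 1. **IPSS.** Re-administer it at the separate pre-procedure visit, where the IIEF is already completed. Name that score as the baseline in the Analysis section, and keep the first score for eligibility only.
2. **Qmax.** If a second pre-treatment flow that plays no part in eligibility is available, use it as baseline. None is listed now, and if one were added at the separate visit, its order relative to cystoscopy would have to be settled. Otherwise report the mean change with a confidence interval as descriptive, state that it includes regression to the mean, and make no significance claim from the qualifying value.
3. **Corrected Qmax estimate.** Show one only as a sensitivity analysis over a stated range of assumed reliability, because a single pre-treatment flow cannot estimate reliability. Report men admitted through retention separately, since the correction does not apply to them.
4. **Interpretation.** State that placebo response and natural change remain uncontrolled, whatever the baseline.

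The cost is a few minutes per patient at a visit already scheduled, some analysis wording, and a slightly smaller reported improvement. Eligibility and treatment rules do not change. One limit remains: a second reading removes only noise that is independent between the two visits, so slower symptom fluctuation would partly persist.

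### The only analysis stated for the safety laboratory measures is a group test of change at p 0.05, which is insensitive to harm confined to a few of 30 men; per-man abnormality counts should be added

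*Combined protocol and SAP*

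**What the plan says.** Under Laboratory Assessment, the plan gives these tests a safety role: "The safety of the therapy will be monitored in part using laboratory analyses, including CBC, serum chemistry, urinalysis, urine culture and PSA". PSA is also treated there as an outcome measure. The baseline work-up includes "Blood chemistry (including blood count, BUN, serum creatinine", and Table 2 repeats blood count and chemistry at 1 week and at 3, 6 and 12 months, with urine testing alongside.

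The Analysis part of item 5 states how the values are handled: "Appropriate parametric and non-parametric tests will be used to assess change in laboratory measures", in one list with flowmetry, IPSS and IIEF. It adds "Appropriate paired parametric and non-parametric tests will be used to determine statistical significance" and "A p value of 0.05 will be considered statistically significant". The tests, visits, analytes and sidedness are not specified. The Statistical Considerations item repeats the testing plan without the laboratory measures.

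The study is small and has one arm: "This is a prospective observational non-comparative study of an initial cohort of 30 patients". The only creatinine threshold we found is an entry exclusion: "Renal insufficiency (serum creatinine of greater than 1.8 mg/dL".

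Safety also has a per-patient route. On adverse events the plan says: "Each adverse event will be recorded as they occur". Each is graded by SIR class, and complications are summarised to the IRB after every 10 patients. The primary outcome is a yes/no judgement for each man on pelvic complications in week 1.

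**The concern.** A paired test of change asks whether the cohort as a whole has moved. That suits PSA, flow rate and symptom scores, where most men are expected to respond. It suits safety laboratory values less well. Item 6 lists iodinated contrast among the non-pelvic risks and puts such risks well below 5%, which is fewer than 0.05 × 30 = 1.5 men. Harm of that kind would be a large change in one or two men and none in the rest. Those men move the mean only slightly, inflate the SD used by the t-test, and add little to a rank sum.

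The text available has no count of men with abnormal values, no shift table and no confidence bound for these measures. The per-patient adverse-event route does not fully close the gap, because no rule says when a laboratory value becomes an event. Kidney and blood-count changes also lie outside the week-1 pelvic primary outcome. They lie outside the stopping rule too, which counts only bladder or rectal injury needing surgery. At stake is how informative the laboratory results will be in a study whose primary goal is safety.

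**Working it through.** The plan gives no power, effect size or SD for laboratory measures, so there is no figure of its own to reproduce.

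**Inputs from the documents.** n = 30; paired tests; significance level 0.05; sidedness not stated.

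**Assumed inputs.** Creatinine rises by 1.0 mg/dL in k men; the change in the others is normal with mean 0 and SD 0.10, 0.15 or 0.20 mg/dL; two-sided testing unless noted.

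**Step 1: a limit that needs no assumed SD or rise.** Let k of n men rise by D, with D so large that variation in the others is negligible.
- Mean change = kD/n.
- Standard error = (D/n) × √[k(n − k)/(n − 1)].
- D cancels, so t tends to √[k(n − 1)/(n − k)].

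For k = 2: √(2 × 29/28) = √2.071 = 1.44. For k = 3: √(3 × 29/27) = √3.222 = 1.79 (1.795 before rounding). The two-sided critical value on 29 degrees of freedom is 2.045. With 2 or 3 men affected, a larger injury therefore does not rescue the two-sided t-test. For k = 2 the limit is also below the one-sided critical value of 1.699.

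**Step 2: simulated miss rates** (n = 30, rise 1.0 mg/dL, 20,000 runs per row; Wilcoxon by normal approximation).

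| Men affected | SD in the others (mg/dL) | t-test, two-sided | t-test, one-sided | Wilcoxon, two-sided |
|---|---|---|---|---|
| 2 | 0.10 | 96% | 82% | 93% |
| 2 | 0.15 | 93% | 80% | 93% |
| 2 | 0.20 | 92% | 80% | 93% |
| 3 | 0.10 | 85% | 49% | 89% |
| 3 | 0.15 | 82% | 57% | 89% |
| 3 | 0.20 | 82% | 63% | 89% |

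**Step 3: sensitivity for 2 men, two-sided.** For rises of 0.3 to 2.0 mg/dL, the t-test misses 91.6 to 99.9% and Wilcoxon 92.9 to 94.6%. For rises of 1 to 20 SDs, the lowest t-test miss rate is 91.3%, at 4 SDs. A sign test misses about 95%. With 27 evaluable men, the t-test misses 91.5 to 99.9%.

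**Step 4: where the test does work.** If all 30 men shift by 0.5 SD, the two-sided paired t-test has 75.4% power. The weakness is specific to harm concentrated in a few men.

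**Step 5: a yes/no laboratory result.** Urine culture is positive or negative, and active urinary infection is excluded at entry. If an exact McNemar test were used and 5 of 30 men (16.7%) became positive with none reversing, p = 2 × 0.5⁵ = 0.0625, which is not significant.

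**Step 6: what counts would show.** 2 of 30 is 6.7%, exact 95% CI 0.8 to 22.1%. For 0 of 30 the two-sided 95% upper limit is 1 − 0.025^(1/30) = 11.6%.

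**The case against.** The strongest reply is that the plan does not make laboratory safety depend on these tests alone. Laboratory values monitor safety only in part. Every visit after treatment has an adverse-event assessment, events are graded per patient down to a class needing no therapy, and all complications go to the IRB after every 10 patients. Two men with a recognised kidney injury would be counted there. This stands. A reader might infer that laboratory safety is decided by the p value, or that a non-significant result will be taken as proof of safety. The documents contain no such rule and do not support either reading. What remains is that recognition depends on someone choosing to call a laboratory value an event.

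The sentence may also be aimed mainly at effectiveness. It groups laboratory measures with flowmetry and symptom scores, and PSA is the only laboratory item among the secondary objectives. That is plausible, but the safety laboratory measures would then have no stated analysis at all.

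Kidney injury is our example. The study says it focuses on pelvic risks, and 2 of 30 (6.7%) is above the rate the plan expects. The miss rates also rest on an assumed rise, SD and absence of drift, and on two-sided testing. A flat claim that the test misses such harm more than 90% of the time is therefore not supported: the one-sided figure is about 80 to 82%, and the rate falls as more men are affected.

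Finally, part of the safety-monitoring section (between the safety tests and the monitoring intervals) was not in the text available, so the absence of a per-man rule is established only for the rest.

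**Conclusion.** The point holds in a limited form. In the text available, a group test of change at p 0.05 is the only analysis stated for the safety laboratory measures, and it is a weak instrument for harm in a few of 30 men. For a 1.0 mg/dL creatinine rise in 2 men, with an assumed SD of change of 0.10 to 0.20 mg/dL in the others, the two-sided t-test misses about 92 to 96% and Wilcoxon about 93%. The limiting t of 1.44 for 2 men shows that the t-test result does not depend on the size of rise chosen. The gap is one of analysis and reporting: it does not touch the primary endpoint or the stopping rule, and per-patient adverse-event recording partly covers it. It is worth correcting because safety is the study's main aim and the remedy uses data already scheduled.

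**What to change.** In the Analysis part of item 5, keep the tests of change as descriptive, since they can still show a cohort-wide shift. PSA stays as an outcome measure. For blood count, chemistry and urine tests, add:

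- a table of shifts from baseline to the worst value after treatment, against the laboratory's normal range;
- the number of men with a new abnormal value, including new positive urine cultures, with an exact 95% confidence interval;
- for creatinine, each man's change from baseline, plus the count above the plan's own 1.8 mg/dL entry limit as a reporting cut-off only. That count alone would not be enough: a man starting at 0.7 who rose by 1.0 would reach 1.7 and not be counted;
- a sentence saying that a non-significant group change is not evidence of laboratory safety.

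The Adverse Events section should also say how a laboratory change comes to be recorded as an event; the criterion is for the investigators to set.

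The cost is a few extra tables and no new data, visits or patients. The results will look less reassuring than a non-significant p value, since even 0 of 30 carries an upper limit of 11.6%, but that is what a study of this size can show.
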